## 7.7 Gastrointestinal Toxicity

Early recognition and treatment of diarrhea and colitis are critical to their management. Patients should be advised to seek medical evaluation if they develop new-onset diarrhea, blood in stool, or severe abdominal pain or if they have worsening of baseline diarrhea. As GI symptoms are common in patients with cancer, it is important that an evaluation/work-up distinguishes between non-drug-related causes (e.g., infection or progression of disease) and a possible drug-related AE as the management can be quite different. Any patient experiencing diarrhea (which may be defined as watery stool, or increase in the frequency stools above Grade 1 with urgency or nocturnal bowel movement, or melena or hematochezia) should be further evaluated for etiology that should include a search for an infectious etiology, *C. Difficile* colitis and other alternative infections as clinically indicated. Consideration should be given to discontinuing medications known to exacerbate colitis.

It is recommended that colitis or enterocolitis of Grade 1 be evaluated as above for other non-immune mediated causes, then monitored closely and treated symptomatically without steroids, including a trial of loperamide may be used. For Grade  $\geq 2$  colitis or enterocolitis, recommendations include endoscopy and/or abdominal CT imaging.

Even if colonoscopy does not reveal gross findings of colitis, biopsies should be performed, and strong consideration should be given to upper endoscopy and biopsies. Patients with gross or

biopsy proven colitis or enteritis should receive IV steroids (recommend 1 mg/kg methylprednisone daily for seven (7) days) followed by a minimum 30-day taper. In patients, with Grade 3 or Grade 4 enterocolitis that does not respond to high dose steroids after seven (7) days, further therapies should be administered as clinically indicated in consultation with gastroenterology subspecialists. Caution should be taken in the use of narcotics in patients with diarrhea, colitis, or abdominal pain as pain medicines may mask the signs of colonic perforation. Consultation with a gastroenterologist should be sought for all moderate- and high-grade cases of GI AEs.

## 7.8 Hepatotoxicity

Concern for immune-mediated liver toxicity may be elicited following LFT elevation of three-fold over baseline and/or right upper quadrant abdominal pain or unexplained nausea or vomiting. Patients should be advised to seek medical evaluation if they notice jaundice (yellow appearance of skin or sclera) or if they develop bruising, bleeding, or right-sided abdominal pain. Physicians should monitor LFTs prior to each nivolumab treatment. As LFT abnormalities are common in patients with cancer, it is important that an evaluation/work-up distinguishes between non-drug-related causes as management may be quite different. Other aetiologies for transaminitis should be considered and evaluated and may include, but are not limited to neoplastic, concurrent medications, viral hepatitis, and other toxic aetiologies. Evaluation for autoimmune aetiologies may be evaluated by ANA, pANC, and anti-smooth muscle antibody tests, as well as hepatology consultation with possible biopsy. Higher-grade hepatic AEs, including drug induced liver illness may be managed with corticosteroids (with or without mycophenolate mofetil).

## 7.9 Pancreatic Toxicity

Pancreatitis has rarely been associated with checkpoint inhibitors and should be considered in cases of abdominal pain associated with elevations of amylase and lipase. Asymptomatic elevations in lipase and amylase have been reported in monotherapy trials. Very few patients reported associated symptoms (e.g., abdominal pain) or radiographic findings (e.g., stranding) consistent with pancreatitis. Thus, there does not seem to be clinical significance to the elevated laboratory values. As lipase/amylase abnormalities are not uncommon in patients with cancer, it is important that an evaluation/work-up distinguishes between non-drug-related causes (e.g.,

progression of disease, concomitant medications, or alcohol) and a possible drug-related cause as the management can be quite different. The recommended management of nivolumab-related elevated lipase/amylase values centers around close observation. Physicians should ensure that patients have no associated symptoms consistent with pancreatitis, such as abdominal pain.

Treatment of pancreatitis should be supportive and may include consultation with gastroenterology subspecialists. Asymptomatic elevations should be monitored approximately on a weekly basis. For sustained asymptomatic Grade 4 elevations and elevated pancreatic enzymes with symptoms consistent with pancreatitis, nivolumab should be discontinued per protocol instructions, and a gastroenterologist should be consulted.

## 7.10 Endocrinopathies

Patients experiencing symptoms such as fatigue, myalgia, impotence, mental status changes, constipation, or other symptoms thought to be associated with endocrine abnormalities should be evaluated for thyroid, pituitary, or adrenal endocrinopathies and an endocrinologist should be consulted. It is possible that events may occur within weeks of beginning treatment, but also after many months (while still on treatment). More than one endocrine organ may be involved and may need to be evaluated. Patients should be advised to seek medical evaluation if they notice new-onset fatigue, light-headedness, or difficulty with vision or if baseline fatigue worsens. As fatigue is common in patients with cancer, it is important that an evaluation/work-up distinguishes between non-drug-related causes, such as progression of disease, anemia, concomitant medications, or depression) and a possible drug-related AE as the management can be quite different.

Patients with Grade 2 hypothyroidism should be evaluated by an endocrinologist for further management. Patients with Grade 2 hypothyroidism adequately managed with thyroid hormone replacement may continue protocol therapy. Patients with Grade 3 or greater hypothyroidism will be removed from the study. These patients should be managed according to *Section 6.11* and evaluation by an endocrinologist is recommended for further management. Patients who enter the study on thyroid replacement should have their medication adjusted to maintain TSH in the normal range.

#### 7.11 Neurologic Toxicity

Neurologic symptoms can manifest as central abnormalities (e.g., aseptic meningitis, encephalopathy, or encephalitis) or peripheral sensory/motor neuropathies (e.g., Guillain-Barre Syndrome, myasthenia gravis complicated with sepsis and fatality). Early recognition and treatment of adverse neurologic reactions is critical to its management. Patients should be advised to seek medical evaluation if they notice impairment in motor function (e.g., weakness), changes in sensation (e.g., numbness), or symptoms suggestive of possible central nervous system abnormalities such as new headache or mental status changes. As neurologic symptoms can be common in patients with cancer, it is important that an evaluation/work-up distinguishes between non-drug-related causes (e.g., progression of disease, concomitant medications, or infection) and a possible drug-related events as the management can be quite different. The principal treatments for neurologic toxicity are dose delay, corticosteroids, and IV immunoglobulin as outlined in the safety algorithm (see *Section 6.9* and sub-sections). For high-grade related neurological symptoms, nivolumab should be discontinued.

## 7.12 Renal Toxicity

Some elevated creatinine and biopsy-confirmed tubulointerstitial nephritis and allergic nephritis have been infrequently observed following treatment with nivolumab. Events were managed with corticosteroids and, in all cases, renal function partially or fully improved.

Physicians should monitor creatinine regularly. As creatinine abnormalities are common in patients with cancer and other comorbidities, it is important that an evaluation/work-up distinguishes between non-drug-related causes (e.g., dehydration, concomitant medications, hypotension, or progression of disease). Corticosteroids and biopsy should be considered as outlined in *Section 6.13* and *6.13.1*.

# 7.13 Autoimmune or Immune System Disorders Effecting Other Organ Systems

Patients experiencing symptoms that may be associated with autoimmune or immune mediated adverse events possibly, probably or definitely related to protocol therapyshould be evaluated and monitored closely. These may include but are not limited to pneumonitis, sarcoid-

like granuloma and neurologic events including hypophysitis, encephalitis, aseptic meningitis, and cranial neuropathy especially cranial nerve seven (CNVII). Consideration should be given to subspecialty consultation particularly if systemic immune suppression is considered.

#### 7.14 Other Immune-Mediated Adverse Events

For suspected immune-related adverse reactions, adequate evaluation should be performed to confirm etiology or exclude other causes. Based on the severity of the adverse reaction, nivolumab should be withheld or discontinued, and corticosteroids administered accordingly. The Study Chair or Co-chair should be consulted. Upon improvement, nivolumab may be resumed after corticosteroid taper. If there is recurrence of any Grade 3 or 4 immune-related adverse reactions or life-threatening immune-related adverse reactions, nivolumab must be permanently discontinued.

Rare cases of myotoxicity (myositis, polymyositis, polymyalgia rheumatica, myocarditis, and rhabdomyolysis) outcome, have been reported with nivolumab. If a patient develops signs and symptoms of myotoxicity, close monitoring should be implemented, and the patient should be referred to a specialist for assessment and treatment without delay. Based on the severity of myotoxicity, nivolumab should be withheld or discontinued after discussion with the Study Chair or Co-Chair, and appropriate treatment instituted. For Grade 3 or 4 myotoxicity, nivolumab should be permanently discontinued.

#### 7.15 Growth Factors

Growth factors that support platelet or white cell number or function can only be administered for culture proven bacteremia or invasive fungal infection. Patients MUST NOT receive prophylactic myeloid growth factor in the first cycle of therapy. The Study Chair or Co-Chair should be notified before growth factors are initiated.

#### 8. EVALUATION SCHEDULE AND DATA TO BE COLLECTED

All clinical and laboratory studies to determine eligibility must be performed within 14 days prior to enrollment in either **Part I, Part II,** or both unless otherwise indicated. Laboratory values used to for inclusion or exclusion criteria purposes (see *Section 4.2* and sub-sections) must be no older than 14 days at the start of therapy. Additional laboratory tests do not need to be repeated if therapy starts within seven (7) days of obtaining lab values for inclusion/exclusion. If a post-enrollment lab value is outside the limits of acceptance, or too old, they must be re-checked within 48 hours prior to initiating therapy; this includes, CBC with differential, bilirubin, ALT/AST and serum creatinine. If the re-check values continue to be outside the limits of acceptance, the patient may not receive protocol therapy. If the laboratory values return to the eligible limits, the patient is permitted to re-enroll if **all** other eligibility criteria are met, including exclusion criteria for concomitant medications and ICIs. In this case, all eligibility laboratory values will have to be repeated. Imaging studies must be obtained within 14 days prior to start of protocol therapy (and the tumour imaging must be repeated, if necessary).

Note: Screening for concurrent malignancies is strongly recommended in patients with confirmed or suspected CMMRD and should be arranged prior to initiation of treatment (see Table 4; Westdorp, 2017). The effectiveness of hematological screening is questionable since non-Hodgkin lymphomas and acute lymphoid leukemia are rapidly growing tumors and surveillance may not improve the outcome for patients with these malignancies (Vasen, 2014; Westdorp, 2017).

**Table 4.** Recommended surveillance protocol for patients with CMMRD (Tabori, 2017).

Examination	Start age	Frequency	Tumours	Comment
MRI brain	At	Q 6 months	CNS tumours	Should not be replaced with WBMRI
	diagnosis			
WBMRI	6 years	Q annually	All tumours	Should not replace dedicated CNS imaging
CBC	1 year	Q 6 months	Leukemia	May be considered
Abdominal U/S	1 year	Q 6 months	Lymphoma	May be considered
				Can be alternated with WBMRI
Upper gastrointestinal endoscopy;	4 to 6 years	Q annually	GI tumours	Upper and lower endoscopy, to increase in
VCE, ileocolonoscopy				frequency when polyps are found
Gynecological exam, transvaginal	20 years	Q annually	GU tumours	As per Lynch syndrome guidelines
U/S, pipelle curettage, UA, dipstick				

Abbreviations: WBMRI = whole body MRI; U/S = ultrasound; VCE = visual capsule endoscopy; GI = gastrointestinal; UA = urine analysis; GU = genitourinary

## 8.1 Study Outline: Part I – Molecular Profiling

Part I Procedures	Pre-Screening Assessment	Screening	Molecular Profiling Assay	Use of Profiling Assay Results	
Window	Prior to screening	Post-informed consent	~2 weeks	Post-assay results & prior to Part II	
	Adm	inistrative procedures			
Part I informed consent/assent 	X	_			
Suspicion of hypermutation 	X				
Eligibility assessment 		X			
Medical History		X			
Stratification 				X	
Relay assay results 				X	
	Labo	ratory investigations			
Provide specimen 		X			
Provide slides for IHC		X			
(optional) 					
TMB assay 			X		
IHC 			X		
Recommended CMMRD work-up (optional) 				X	

<sup>1 A separate informed consent must be obtained for **Part I** and **Part II** (when eligible). All eligible patients must undergo study **Part I**, except for those with a TMB assay report from a previously obtained specific CLIA-certified laboratory already (see *Lab Manual*).

<sup>2 See Section 4.2.1 for a detailed description of eligible recurrent or relapse paediatric cancer patients suspected to be hypermutant.

<sup>3 See Section 4.2.1 for a list of **Part I**: Molecular Profiling inclusion criteria.

<sup>4 Patients with applicable TMB levels will be stratified in to cohorts as follows: A) TMB  $\geq$ 5 but <10 mut./Mb; B) TMB  $\geq$ 10 mut./Mb; C) unknown TMB in patient/unobtainable tissue for a patient with RRD (see *Section 4.2* for details).

<sup>5 The results of the TMB assay obtained from an individual's participation in **Part I** of the study may be disclosed with his/her consent to his/her health care providers for the purpose of obtaining appropriate medical care, as well, this information will be relayed back to the patient, their parents/ legal guardian, their attending local physician and the clinical trial team. Patients with eligible results will be asked to sign a different **Part II**-specific informed consent prior to **Part II** screening.

<sup>6Neoplastic specimen will be necessary for enrollment to **Part I** (see *Lab Manual* for details). If remaining tissue exists, it may be retained for possible use in **Part II** companion biomarker studies, if the patient consents to **Part II** and for the tissue use specifically. If the patient does not qualify for enrollment in **Part II** or does not wish to participate in the tumour tissue portion of the companion biomarker studies for **Part II**, remaining whole tissue will be returned to the local physician upon request. Tissue will not be biopsied/obtained for the sole purpose of the study.

<sup>7&9 Recommended for all patients with suspected or confirmed RRD only and/or no available tissue available for TMB assay; not mandatory as specified in *Section 3.5* and *Lab Manual* for details. Patients may optionally provide tissue for IHC assessment of MMR gene protein expression for diagnostic purposes relevant to the study at the discretion of the Study Chair or Co-chair, Patients with confirmed or suspected CMMRD should undergo regular tumour surveillance according to published guidelines.

<sup>8 TMB analysis must be performed in a Study Chair or Co-chair approved, CLIA-certified laboratory

<sup>10\*Optional\* Patients with confirmed or suspected CMMRD should undergo regular tumour surveillance according to published guidelines. See *Section 8.0: Table 4* for recommended surveillance to be performed prior to enrollment in **Part II**.

## 8.2 Study Calendar: Part II – Treatment and Companion Biomarker Studies

PART II	Pre- Treatment	Cycle 1			Subsequent cycles			Post- treatment		
	Screening	D1	D8	D15	D22	D1	D15	End of Tx visit	Safety Visit 	Follow- up 
Window	-14d	n/a	±2d	±2d 	±2d	±2d 	±2d 	n/a	± 7d	± 14d
		l	Aa	lministrative	procedures	I			I	l
Part II Informed	X									
consent/assent1										
Inclusion/exclusion criteria	X									
Medical History	X									
Nivolumab administration 		X		X		X	X			
AE evaluation					Conti	nuously thro	ughout	l		
Concomitant meds						nuously thro				
	l .			Clinical Asse						
Physical exam	X	X	X	X	X	X	X	X	X	X
Vital signs 	X	$X^3$	X	$X^3$	X	X	$X^3$	X	X	X
Neurological exam 	X	X 				X			X	X
Height and weight 	X	Weight only		Weight only		X	Weight only	X	X	X
Performance status	X	-				X			X	X
Evaluation of Tanner stage 	X									
Evaluation of menstrual status 	X									
	•	•	Labora	tory/Imaging	investigatio	ns 	•	•	•	•
Pregnancy test 	X	X				X				
CBC with differential 	X	X 	X	X	X	X	X		X	X
Biochemistry 	X	X 	X	X	X	X	X		X	
Amylase, lipase, CRP	X					X			X	
TSH 	X					X		12	X	12
Disease assessment 	X					$(X)^{12}$		X 		X 
PET-CT or full body	X									
MRI (including head) 	v									
Colonoscopy 	X			ompanion B	iomankous		L	L		
Tumour Tissue 	X 		 	ompanion Di	omurkers	$(X)^{14}$				
Blood for DNA		X 				(21)				
Blood for RNA		X 								
Blood for lymphoblast		X 								
cell line establishment										
Blood for circulating		X 				X		X		X
tumour DNA, processed immediately 										
Blood extracted for PBMCs, processed immediately 		X 		X		X		X		X

-  A separate informed consent must be obtained for **Part I** and **Part II** (when eligible). All eligible patients must undergo study **Part I**, except for those whom possess a TMB assay report from the specific CLIA-certified laboratory (see *Lab Manual*) and directly begin screening for **Part II**.
- $^2$  All eligible patients will receive nivolumab at the dose of 3 mg/kg once every 14 days  $\pm$  2 days; on approximately days 1 (D1) and 15 (D15) of each cycle. Two doses comprise one cycle. Nivolumab will be administered as a 60-min +/- 10 min infusion. Refer to Section 5.1 and 9.8 for dosing and administration details, respectively. The dosing calculations should be based on the actual body weight in kilograms and may be calculated using the weight obtained at the previous dose administration. If the patient's weight on the day and prior to drug administration differs by >10% from the weight used to calculate the dose, the dose should be recalculated. All doses should be rounded to the nearest milligram. There will be no dose modifications allowed. Any dose delays or omissions should be discussed with the Study Chair or Co-chair prior to the scheduled administration date. An exception made during an emergent circumstance should be discussed with the Study Chair or Co-chair as soon as possible.
- $^3$  Vital signs (HR, RR, BP, temperature, and pulse oximetry) and assessment of AEs (e.g. rash) are to be performed pre-dose and every 15  $\pm$  5 minutes during administration of study drug. At the completion of infusion, vital signs are to be performed every 15  $\pm$  5 min twice then every 30  $\pm$  5 min x 3 times. Following completion of cycle 1 and in patients who have tolerated nivolumab without infusion reactions, frequency of vital signs evaluation following infusion may be reduced at the discretion of, and documented by, the treating physician.
-  Neurological exams will be required only for patients with brain tumours or when CNS-specific concerns arise.
-  The dosing calculations should be based on the actual body weight in kilograms and may be calculated using the weight obtained at the previous dose administration. If the patient's weight on the day and prior to drug administration differs by >10% from the weight used to calculate the dose, the dose should be recalculated. All doses should be rounded to the nearest milligram. There will be no dose modifications allowed.
-  Refer to Section 21 (Appendix III) for Tanner Staging.
- Female patients only.
- $^8$  Women of childbearing potential (WOCBP; and those with Tanner stage of ≥ 3) must have a negative pregnancy test every 4 weeks. During the **Part II** screening window (-14 days), WOCBP must have a negative serum pregnancy test. WOCBP must have a negative serum or urine pregnancy test (minimum sensitivity 25 IU/L or equivalent units of HCG) within 24 hours prior to the start of nivolumab administration and must be willing to adhere to effective contraception during treatment and for 5 months after the last dose of nivolumab. Males who are sexually active with women of childbearing potential must be willing to adhere to effective contraception during and for 7 months after the last dose of nivolumab. Abstinence is an acceptable method of birth control. Additional pregnancy tests (serum or urine) should be obtained during treatment in accordance with institutional guidelines.
-  If patients have Grade 4 neutropenia then CBCs should be checked twice weekly or as clinically indicated until recovery to Grade 3 or until meeting the criteria for removal from the study.
-  Biochemistry includes: sodium, potassium, calcium, chloride, phosphate, magnesium, serum creatinine, BUN (urea), bilirubin (conjugated/unconjugated or total), ALT and AST.
-  Free T4 should also be measured for patients with an abnormal TSH level. Guidance on the management of patients who develop hypothyroidism is included in *Section 7.10*. TSH will be assessed at end of each cycle, within 3 days prior to the next cycle.
-  During the study, disease evaluations will be done at end of cycle 1 (window of -7 days) and every two (2) months (window of -7 days) as per *Section 10* applicable response evaluation criteria. Tumour disease assessments will also be done at end of treatment visit (window of +/-7 days) and once every three (3) months (window of +/-14 days) during follow-up for 1 year. Tumour disease assessments during follow-up may be performed at referring hospital. Evaluations required will depend on patient diagnosis. For patients with solid tumours, CT or MR imaging of appropriate sites is mandatory. For patients with leukaemia, BM evaluation is adequate.
-  Recommended for patients with confirmed or suspected CMMRD only; not mandatory. Regardless of study participation, patients with confirmed or suspected CMMRD should undergo regular tumour surveillance according to published guidelines (see *Section 8, Table 4*, Tabori, 2017).
-  Tissue provided in **Part I** may be used for *Companion Biomarker* studies with patient consent. Whenever possible, additional samples will be obtained for biological analyses in the event that a patient requires surgery/a biopsy after starting treatment and cancerous tissue is removed. Tumour will be only biopsied/ surgically removed for medical/ diagnostic purposes and not specifically for the purposes of the study. When possible (with patient consent), please contact Study Chair or Co-Chair as well as refer to *Lab Manual* prior to surgery/ biopsy acquisition while on study to facilitate time and preservative-sensitive sample processing.
- Blood for circulating tumour DNA (ctDNA) is required at baseline, at the end of Cycle 1, but prior to C2D1 dose (window -7 days from C1D28), every two (2) months at the end of the cycle prior to the subsequent CXD1 dose (window -7 days from CXD28 of the previous cycle) during the study, at the end of study visit and every 3 months subsequently (window ± 14 days) during follow up for 1 year (i.e. at the times of disease re-evaluation). To be extracted and processed immediately on same day (as per *Lab Manual*). All *Companion Biomarker* assays must be performed approximately 4 weeks after CXD1, irrespective of any dose omissions or delays. The results of these assays should reflect the effect of the two former doses, not the status at CXD1. All attempts to compile blood draws to visit dates prior to drug administration should be made.
- Blood extracted PBMCs for T-cell functional studies are required at baseline, on Cycle 1, Day 15 (C1D15; window –7 days), at the end of Cycle 1, but prior to C2D1 dose (window -7 days from C1D28), every month at the end of the cycle, prior to the subsequent dose

(window -7 days from CXD28 of the previous dose) during the study, at the end of study visit and every 3 months (window  $\pm 14$  days) during follow up for 1 year. To be extracted and processed immediately on same day (as per *Lab Manual*). All *Companion Biomarker* assays must be performed approximately 4 weeks after CXD1 (excluding the C1D15 blood sample), irrespective of any dose omissions or delays. The results of these assays should reflect the effect of the two former doses, not the status at CXD1. All attempts to compile blood draws to visit dates prior to drug administration should be made

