## 6.2 Dose Modifications for Non-Haematological Toxicity

Patients who have any Grade 3 or Grade 4 non-hematological toxicity attributable to the investigational drug with the specific exclusion of the following, will be removed from the study:

- Grade 3 ALT that returns to levels that meet initial eligibility criteria or baseline within seven (7) days and does not require systemic immunosuppression;
- Grade 3 liver enzyme elevation, including AST/GGT that returns to baseline within 7 days and does not require systemic immunosuppression;
- Grade 3 or 4 serum electrolyte or mineral abnormalities responsive to supplementation;
- Grade 3 or 4 amylase or lipase abnormalities that are not associated with diabetes mellitus (DM), associated liver or gall bladder inflammation or clinical manifestations of pancreatitis;
- isolated Grade 4 amylase or lipase abnormalities that are not associated with symptoms or clinical manifestations of pancreatitis and decrease to < Grade 4 within 1 week of onset;
- Grade 3 rash/oral lesions that resolves to Grade  $\leq 1$  within seven (7) days;
- Grade 3 or 4 seizures (multiple seizures despite medical intervention or life-threatening seizures/status epilepticus) that may occur in the context of pseudo-progression;
- fever greater than 40°C of ≤24 hr. duration;
- Grade 3 fatigue that resolves to Grade  $\leq 2$  within 7 days;
- Grade 3 creatinine increase that resolves to Grade  $\leq 1$  or baseline within seven (7) days.

Patients who experience the following non-hematological toxicities attributable to protocol therapy will also be removed from the study:

- Grade 2 fever that does not resolve to Grade  $\leq 1$  within seven (7) days;
- Grade 2 uveitis, eye pain or blurred vision that does not respond to topical therapy and does not improve to Grade 1 prior to next scheduled dose;
- Grade 2 non-hematological toxicity requiring systemic immunosuppressive therapy. This includes, but is not limited to, autoimmunity of the lung, heart, kidney, bowel, CNS, pituitary or eye;
- Grade 2 endocrine toxicity requiring hormone replacement, with the exception of Grade
   2 hypothyroidism, thyroiditis and thyroid dysfunction adequately managed with thyroid hormone replacement;
- Grade 2 adrenal insufficiency;
- Grade 3 colitis or Grade 3 diarrhea attributable to protocol therapy of more the seven (7) days of duration.

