# 6.5 Dose Modifications for Hepatic/Pancreatic Adverse Events

Liver Function	Management/Next Dose of Nivolumab	
Elevation		
Grade 1	Continue protocol therapy.	
Grade 2	Hold until laboratory values return to baseline and management with corticosteroids, if needed, is completed.	
Grade 3 – 4	Off protocol therapy.	

Continued treatment of active immune-mediated hepatitis may exacerbate ongoing inflammation. Holding drug to evaluate LFT changes and early treatment are recommended.

LFT changes may occur during steroid tapers from other events and may occur together with other GI events including cholecystitis/pancreatitis.

**Recommended management:** See for Hepatic AE Management Algorithm (Section 6.5.1).

Pancreatitis; enzyme elevations CTCAE v.4.03	Management/Next Dose of Nivolumab
Grade 1	Continue protocol therapy.
Grade 2 Amylase elevation or radiological findings only.	Continue protocol therapy.
Grade 2 Pancreatitis and/ or lipase elevation or radiological findings only.	Hold until baseline; Resume at same dose level if asymptomatic.
Grade 3 Severe pain; Vomiting;	• Hold protocol therapy until recovery ≤ grade 1 unless exception in Section 6.2 is met.

Medical intervention	
indicated (e.g. analgesia,	
nutritional support above	
baseline).	
Grade 4	$ullet$ Hold off protocol therapy until recovery to baseline or $\leq$
Life threatening	Grade 1.
consequences;	
Urgent intervention	
indicated.	

Patients may develop symptomatic and radiologic evidence of pancreatitis as well as DM and DKA. Lipase elevation may occur during the period of steroid withdrawal and with other immune mediated events or associated with colitis, hepatitis, and patients who have asymptomatic lipase elevation typically have self-limited course and may be retreated.

**For treatment management** of symptomatic pancreatitis please follow the Hepatic Adverse Event Management Algorithm below (see *Section 6.5.1*).

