#### 12.6 Follow up on Adverse and Serious Adverse Events

For the SAEs that have been deemed by the investigator as unrelated to protocol treatment, the SAE reporting period begins on the first date of treatment and ends on the date of Safety Visit or 100 days after discontinuation of the study drug, whichever is later. For the SAEs that have been deemed by the investigator as at least possibly related to protocol treatment, the SAE must be reported even if this occurs after the date of scheduled Safety Visit or past 30 days after discontinuation of the study drug.

The investigator shall provide follow-up information in a new follow-up SAE form. All SAEs must be followed until resolved, become chronic, or stable unless the patient is lost to follow up. Resolution status of such an event should be documented on the eCRF.

The eCRF should capture all AEs occurring from cycle 1 day 1 till the date of Safety Visit or 100 days after discontinuation of the study drug, whichever is later.

In addition, any known untoward event of any severity that occurs subsequent to the AE reporting period that the Investigator assesses as at least possibly related to the protocol therapy (i.e., the relationship cannot be ruled out) should also be reported as an AE.

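### Glucose is never scheduled although diabetes is a named toxicity on which a removal exception depends, and scheduled chemistry, amylase/lipase and thyroid tests end about day 30 although adverse events are collected to day 100

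*Protocol*

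**What the plan says.** **Panel.** Protocol 8.2, footnote 10: "Biochemistry includes: sodium, potassium, calcium, chloride, phosphate, magnesium, serum creatinine, BUN (urea), bilirubin", followed by ALT and AST. The list is closed. The other safety laboratory rows are CBC, TSH, pregnancy test and "Amylase, lipase, CRP"; none contains glucose or HbA1c.

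**Diabetes elsewhere in the protocol.**
- 6.5: "Patients may develop symptomatic and radiologic evidence of pancreatitis as well as DM and DKA".
- 6.11.1 has an instruction for symptomatic diabetes, with blood sugar monitoring once it has appeared.
- 4.2.2 says that patients with glucose intolerance should be monitored, without naming a test or a time.
- 6.2 lists exceptions to removal. One covers Grade 3 or 4 "amylase or lipase abnormalities that are not associated with diabetes mellitus (DM"), and adds liver or gall bladder inflammation and clinical pancreatitis as further conditions. The Grade 3 pancreatic row in 6.5 refers back to the 6.2 exceptions.

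**When testing ends.** Biochemistry, amylase/lipase and TSH are last marked at the Safety Visit, which footnote 20 sets at 30 days after the last dose with a 7-day window either side. The Follow-up column (every 3 months for a year, ± 14 days) marks CBC, physical examination, vital signs and performance status, but none of these three. For thyroid function the footnote ties testing to dosing: "TSH will be assessed at end of each cycle, within 3 days prior to the next cycle".

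**When event collection ends.** 12.6: "The eCRF should capture all AEs occurring from cycle 1 day 1 till the date of Safety Visit or 100 days" after discontinuation, whichever is later. The synopsis adds that every laboratory toxicity of Grade 3 or above is collected.

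**The concern.** Describing toxicity is a secondary objective (2.2), and for liver, kidney, pancreas, thyroid and glucose much of it is defined by laboratory values. An event of that kind that causes no symptoms enters the database only if someone draws the test.

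Two things follow. First, hyperglycaemia has no scheduled route into the data at any time, and the diabetes condition in 6.2 has no scheduled result behind it. Second, after about day 30 the protocol goes on collecting events without the tests that would reveal the silent ones. A table showing no hepatic, renal, pancreatic or thyroid laboratory toxicity between the Safety Visit and day 100 could mean that none occurred or that none was looked for, and the data could not tell these apart.

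**Working it through.** The plan states no figure to reproduce. The check sets the calendar against the sections that depend on it, with simple arithmetic.

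**Glucose**

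Inputs: maximum treatment 24 months and 28-day cycles (5.1); biochemistry marked at screening, Cycle 1 days 1, 8, 15 and 22, days 1 and 15 of later cycles, and the Safety Visit (8.2).

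- Cycles in 24 months: 730 / 28 = 26.1, so 26.
- Panel draws: 1 (screening) + 4 (Cycle 1) + 25 × 2 (later cycles) + 1 (Safety Visit) = 56. This is 55 if the Cycle 1 day 1 draw is waived under footnote 17.
- Glucose results among them: 0.

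| Section | What it needs | What 8.2 supplies |
|---|---|---|
| 6.2, amylase/lipase exception | whether diabetes is associated | amylase and lipase, no glucose |
| 6.5 | recognition of diabetes and ketoacidosis | nothing scheduled |
| 6.11.1 | blood sugar once diabetes is symptomatic | nothing scheduled |
| 4.2.2 | monitoring of glucose-intolerant patients | nothing scheduled |

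A separate 6.2 bullet, for isolated Grade 4 enzyme rises that settle within a week, does not mention diabetes. The dependence is therefore on one of two overlapping exceptions.

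**After treatment**

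Inputs: Safety Visit at day 30 ± 7 (8.2); event collection to day 100 when that is the later date (12.6). I take last dose (footnote 20) and discontinuation of drug (12.6) as the same day. In the text available the TSH row carries stray 12s; I read them as footnote numbers belonging to the disease assessment row, so TSH is not marked at follow-up.

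- Last scheduled test: 30 − 7 = day 23 to 30 + 7 = day 37.
- Days with event collection but no scheduled test: 100 − 37 = 63 to 100 − 23 = 77; nominally 100 − 30 = 70.

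Against the whole collection window, which opens at Cycle 1 day 1, the share depends on treatment time T:

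- At T = 730 days: 70 / (730 + 100) = 8.4% (63 / 830 = 7.6% to 77 / 830 = 9.3%).
- The gap exceeds half the window only if T < 2 × gap − 100, that is T below 26, 40 or 54 days for gaps of 63, 70 and 77.

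**First follow-up visit**

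Three months is about 91 days. Counted from the last dose, the visit falls at 91 ± 14 = day 77 to 105. Counted from a Safety Visit on day 30, it falls at 121 ± 14 = day 107 to 135. The protocol does not say which origin applies.

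**The case against.** The strongest reply is that nothing here is a contradiction. Section 12.6 sets a reporting period and promises no laboratory surveillance to its end; 12.1 makes a laboratory value an adverse event when it leads to discontinuation, treatment or intervention, or is judged clinically important; and how long to schedule chemistry after treatment is a design choice. That stands: the point is about ascertainment, not a broken rule.

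It is also true that adverse events are evaluated continuously, that follow-up visits include examination, vital signs and CBC, that required observations continue after removal until the planned end of the cycle or until known events resolve (13.2), and that related events remain reportable after the window closes. A reader might infer that late organ toxicity goes undetected. The documents do not support that: symptomatic events have several routes in, and only silent ones lack a systematic route.

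A reader might also infer that a patient with new diabetes would be kept on drug under an exception that does not apply. That too goes beyond the text. The exception arises only after a Grade 3 or 4 enzyme result, 7.9 asks for a work-up of its cause, and nothing prevents an unscheduled glucose. What remains is that the condition rests on tests the protocol does not schedule.

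The post-treatment part is weaker for some organs. Section 7.9 doubts the clinical significance of asymptomatic enzyme rises, and 7.10 speaks of late endocrine events while patients are still on treatment.

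**Conclusion.** The point holds as a cheap improvement to safety ascertainment. The glucose gap is the stronger part, since it runs through all treatment: about 56 scheduled panels over 24 months, none with glucose, in a protocol that names diabetes as a toxicity and uses it as a condition. Asymptomatic hyperglycaemia may be missed.

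The second part is narrower: 63 to 77 of the 100 post-treatment days have no scheduled biochemistry, amylase/lipase or TSH, so asymptomatic toxicity in that stretch may be under-ascertained. It would be wrong to say that most of the adverse event window is untested. The window opens at Cycle 1 day 1 and the panel is drawn at each dosing visit, so for a patient treated for 24 months the gap is about 8% to 9% of it.

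The sizes rest on treating last dose and discontinuation as one day, on 24 months as about 730 days, and on reading the TSH row as unmarked at follow-up. The documents give no event rate from which to estimate how many events would be missed.

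**What to change.** 1. In 8.2, add glucose to the footnote 10 panel wherever that panel is already drawn.
2. Add the biochemistry panel, amylase/lipase and TSH to the first follow-up visit, where CBC is already drawn, and state the origin from which that visit is timed. Otherwise, state in the safety reporting that laboratory toxicity after the Safety Visit is not systematically ascertained. One added draw narrows the gap without closing it, and it falls inside the 100 days only under some readings of the origin.
3. Reconcile 8.2 with 12.6, with the diabetes wording in 6.2, 6.5 and 6.11.1, and with 13.3, which lists 30 days after the last dose as an off-study criterion although follow-up runs for 12 months. Which removal or management rule should apply is for the clinical authors.

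Cost: a small assay charge, slightly more blood (patients may be as young as 12 months) and a few more laboratory adverse events to report. Disease assessment, ctDNA and PBMC samples follow the same 3-monthly schedule, so stating its origin should be checked against them.
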